- Change in waist circumference from baseline to week 48
- Change in seated systolic BP and seated diastolic BP from baseline to week 48
- Change in seated systolic BP and seated diastolic BP from baseline to week 48 in patients with baseline seated systolic BP >140 mmHg
- Percent change in total cholesterol (TC), low density lipoprotein cholesterol (LDL-C), high density lipoprotein cholesterol (HDL-C), triglycerides (TG) and free fatty acids (FFA) from baseline to week 48

Variables for the long-term, double-blind extension period II

- AEs, laboratory values, ECG, pulse, BP, hypoglycaemic events, calculated creatinine clearance, eGFR, total protein/creatinine ratio (mg/g) and physical examination findings (e.g. oedema) from baseline to week 104, and from week 48 to week 104
- Change in HbA1c from baseline to week 104.
- Change in HbA1c from week 24 to week 104.
- Change in HbA1c from week 48 to week 104.
- Change in FPG from baseline to week 104 and from week 48 to week 104..
- Change in body weight from baseline to week 104, and from week 48 to week 104.
- Proportion of patients with calculated mean daily insulin dose reduction from baseline to week 104, and from week 48 to week 104.
- Mean change and percentage change in calculated mean daily insulin dose from baseline to week 104

- Mean change and percentage change of calculated mean daily insulin dose from week 48 to week 104.
- Change in HbA1c from baseline to week 104, and from week 48 to week 104 in patients with a HbA1c of $\geq 9\%$ at baseline
- Proportion of patients achieving HbA1c $< 7\%$ at week 104 and from week 48 to week 104
- Change in HbA1c from baseline to week 104, and from week 48 to week 104 in patients with a HbA1c of $\geq 7.5\%$ and $< 9\%$ at baseline
- Change in HbA1c from baseline to week 104, and from week 48 to week 104 in patients with BMI ≥ 27 kg/m² at baseline
- Change in HbA1c from baseline to week 104, and from week 48 to week 104 in patients with BMI ≥ 30 kg/m² at baseline
- Change in body weight from baseline to week 104, and from week 48 to week 104 in patients with a baseline BMI ≥ 30 kg/m²
- Change in body weight from baseline to week 104, and from week 48 to week 104 in patients with a baseline Body Mass Index (BMI) ≥ 27 kg/m²
- Change in waist circumference from baseline to week 104, and from week 48 to week 104
- Change in seated systolic BP and seated diastolic BP from baseline to week 104, and from week 48 to week 104

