After 24 weeks of double-blind treatment, patients will continue in the randomized double-blind extension period with the same treatment given as at the end of the 24-week double-blind treatment period. Patients will return for visits approximately every 8 weeks to assess efficacy and safety of the treatment. The patients will be instructed to record their fasting SMBG as well as insulin use daily. The patients will further be instructed to always self-monitor plasma glucose in case of symptoms suggestive of hypoglycaemia and to register any signs of hypoglycaemia in the supplied diary. During the study treatment the patients will be instructed to keep their insulin (and if applicable OAD) dosage unchanged.

Up-titration is defined as an increase in mean daily insulin dose that meets both of the following criteria:

1. the increase in insulin dose is more than 5 IU (i.e. 6 IU or greater)

and

2. the increase in insulin dose is greater than 10% of the baseline insulin dose.

Any insulin dose changes (even if more than 5 IU/ day or more than 10% of the mean daily insulin dose at baseline) during hospitalisation is not considered as an up-titration as long as the insulin dose change is not for a period of more than 10 days and the primary reason for hospitalisation is not management of the patient's glycaemic control. Similarly, if insulin requirement has increased temporarily, e.g. due to an infection, it will not be considered an up-titration even if the insulin dose increase is more than 5 IU or more than 10 % of the baseline mean daily insulin dose as long as such an increase is for a period of not more than 10 days and the insulin dose is expected to return to the baseline level once the precipitating condition has resolved.

Up-titration of the insulin dose during the 24-week double-blind extension period shall be considered by the investigator under the following circumstances:

- if HbA1c measured by central laboratory exceeds 8% at any point of the 24 weeks double-blind extension period

or

- if the FPG measurement taken at the site visits exceeds 180 mg/dl (9.9 mmol/l) and this FPG result is confirmed by both the central laboratory and a repeat FPG measurement at the site at a return visit within 72 hours

or

- if at least 3 fasting SMBG diary measurements from the past 7 days exceed 180 mg/dl (9.9 mmol/l). Diary fasting SMBG values that meet these criteria should be recorded in the eCRF.

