Insulin dose should not be uptitrated if both the following scenarios are met:

1. A patient has experienced unexpected hypoglycemic event/s

and

2. An uptitration of insulin may put the patient at an increased risk of hypoglycaemia in the clinical opinion of the investigator.

An unexpected hypoglycemic event is an hypoglycemic event that cannot be explained by circumstances such as missing a meal, or extensive physical exertion.

If a patient experiences an unexpected hypoglycemic event in spite of high FPG or HbA1c levels, the investigator should consider a change in timing of the insulin dose and/or a change of the insulin regimen, rather than considering up-titration of the insulin dose.

The last HbA1c and FPG values measured by central lab prior to the up-titration of the insulin dose will be carried forward for the efficacy analyses at week 48.

Reduction of insulin dose shall be ordered by the investigator if the patient reports two of more readings of plasma glucose value ≤ 70 mg/dl (≤ 3.8 mmol/l). In addition, the investigator may consider an insulin dose adjustment (dose reduction or change in timing of insulin dose) in patients who report symptoms suggestive of hypoglycaemia without confirmatory glucose measurements if, in the opinion of the investigator, the patient is at increased risk of further hypoglycemic episodes without such insulin dose adjustments.

Patients should be encouraged to contact the investigator in such a case to allow the reduction of insulin dose.

Background OAD therapy may only be decreased if a concern of hypoglycaemia arises in a patient that has already been completely taken off of insulin.

Background OAD therapy may not be increased at any time during the study.

Patients will be discontinued from the study if after they have had complete withdrawal of both insulin and if applicable other OAD, they subsequently experience more than one event of major hypoglycaemia, and the investigator decides that current treatment poses the patient at risk of either repeated hypoglycaemic events or major hypoglycaemia. Major hypoglycaemia is defined as a symptomatic event requiring external assistance due to severe impairment in consciousness or behaviour with a capillary or plasma glucose value < 3 mmol/l (< 54 mg/dl) and prompt recovery after glucose or glucagon administration.

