If a patient experiences an unexpected hypoglycemic event in spite of high FPG or HbA1c levels, the investigator should consider a change in timing of the insulin dose and/or a change of the insulin regimen, rather than considering uptitration of the insulin dose.

The last HbA1c and FPG values measured by central lab prior to the up-titration of the insulin dose will be carried forward for the efficacy analyses at week 104.

Reduction of insulin dose shall be ordered by the investigator if the patient reports two or more readings of plasma glucose value ≤ 70 mg/dl (≤ 3.8 mmol/l). In addition, the investigator may consider an insulin dose adjustment (dose reduction or change in timing of insulin dose) in patients who report symptoms suggestive of hypoglycaemia without confirmatory glucose measurements if, in the opinion of the investigator, the patient is at increased risk of further hypoglycemic episodes without such insulin dose adjustments.

Patients should be encouraged to contact the investigator in such a case to allow the reduction of insulin dose.

Background OAD therapy may only be decreased if a concern of hypoglycaemia arises in a patient that has already been completely taken off of insulin. If background OAD therapy needs to be reduced, the last HbA1c and FPG values measured by the central laboratory prior to the reduction in other OAD dose will be carried forward for the efficacy analyses at week 104.

Background OAD therapy may not be increased at any time during the study.

Patients will be discontinued from the study if after they have had complete withdrawal of both insulin and if applicable other OAD, they subsequently experience more than one event of major hypoglycaemia, and the investigator decides that current treatment poses the patient at risk of either repeated hypoglycaemic events or major hypoglycaemia. Major hypoglycaemia is defined as a symptomatic event requiring external assistance due to severe impairment in consciousness or behaviour with a capillary or plasma glucose value < 3 mmol/l (< 54 mg/dl) and prompt recovery after glucose or glucagon administration.

Randomized patients who discontinue early should complete the procedures described for visit 18 (end of treatment period) immediately following discontinuation of study drug. Thereafter patients should return for the 3 week follow up visit so that visit 19 procedures can be completed.

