6.3 Description of analysis sets

Two analysis sets are specified for efficacy, the full analysis set and the per-protocol analysis set. The primary efficacy variable of change from baseline in HbA1c will be reanalyzed using the per-protocol analysis set if more than 10% of the subjects in any regimen are found to significantly violate the terms and conditions of the protocol. Otherwise, efficacy analysis will be restricted to the full analysis set. These analysis sets and the safety analysis set are described as follows.

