6.3.1 Full analysis set

The full analysis set will include all randomized subjects (as randomized) who received at least one dose of study medication during the 24-week double-blind treatment period, who have a non-missing baseline value and at least one post-baseline efficacy value for at least one efficacy variable during the 24-week double-blind treatment period. The intention-to-treat principle will be preserved despite the exclusion of subjects who took no study medication, as the decision of whether or not to begin treatment during the randomized treatment period could not be influenced by knowledge of the assigned treatment. Missing values will be replaced by the last observation carried forward (LOCF) approach.

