6.4 Method of statistical analysis

6.4.1 Analysis of primary and secondary efficacy for the 24-week treatment period

The primary and secondary efficacy analyses will be based on the full analysis set. The primary endpoint may also be analyzed with the per-protocol analysis set. Treatment effects will be determined through pair-wise treatment group comparisons: each dapagliflozin treatment group versus placebo. No statistical comparisons will be made amongst the dapagliflozin groups.

For endpoints not examining insulin dose, the last post-baseline measurement prior to the first up-titration will be used for subjects whose insulin dose is up-titrated (i.e., patients are censored at the time of up-titration). Endpoints examining insulin dose will also use LOC, but without censoring at the time of titration. To directly assess the relationship between changes in insulin dose and HbA1c, changes in HbA1c will also be summarized using the observations from the same time points as analyzed for insulin dose as a supportive analysis.

The change from baseline to week 24 in HbA1c will be analyzed using an analysis of covariance model (ANCOVA) with factors for treatment group and use of other OADs as fixed effects, and covariate for baseline HbA1c. The model will be used to derive least squares estimates of the treatment differences (each dapagliflozin dose group versus placebo) in mean change with corresponding p-value and two-sided 95% confidence interval. Further, two-sided 95% confidence intervals for the mean change within each treatment group will be calculated.

To preserve the Type I error rate ≤ 0.050 (two-sided) across the primary and within each dose group for the four key secondary endpoints, a hierarchical step-wise procedure will be used to interpret the statistical significance of these treatment comparisons. The details of the step-wise procedure are provided in Section 6.2.

Continuous secondary efficacy variables will be analyzed by means of an ANCOVA for change from baseline using treatment group and use of other OADs as fixed effects and baseline value as a covariate. By analogy to the primary efficacy variable, the model will be used to derive point estimates and two-sided 95% confidence intervals for the mean change within each treatment group as well as for the difference in mean change between the dapagliflozin and placebo groups. Nominal p-values for the difference between the treatment groups will be provided.

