6.4.2 Analysis of efficacy during the long-term, double-blind extension period I and II

All variables to be analyzed at week 24 will be re-examined at the week 48 and 104 time point. Further, changes from week 48 to week 104 will be analyzed (see Section 4.6). In addition, the change in HbA1c levels from week 24 to week 48 and 104, and from week 48 to week 104 will be evaluated (see Section 4.6). In general, the same statistical methodology as described for the 24-week treatment period will be used for data in the long term double-blind extension period I and II. Summaries will be limited to point estimates and 95% confidence intervals.

For extension period II, summaries will be provided by the original, randomized treatment groups although selected analyses will also provide results for the pooled group of all patients who received 10 mg during this period

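### Carrying one value forward to both week 48 and week 104 makes the week 48 to week 104 change exactly zero by rule for patients whose last usable value is at or before week 48

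*Protocol*

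**What the plan says.** Section 3.1 sets the carry-forward rule separately for each period. For extension period I, the last HbA1c and FPG results "prior to the up-titration of the insulin dose will be carried forward for the efficacy analyses at week 48". For extension period II, the corresponding results "prior to the up-titration of the insulin dose will be carried forward for the efficacy analyses at week 104".

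Section 6.4.1 states which up-titration counts and widens the scope to all endpoints that do not examine insulin dose: "the last post-baseline measurement prior to the first up-titration will be used for subjects whose insulin dose is up-titrated". For patients with missing data, Section 6.3.1 says "Missing values will be replaced by the last observation carried forward (LOCF) approach". Membership of the full analysis set depends only on the first 24 weeks, so a patient who leaves later stays in it. On the use of the per-protocol set, Section 6.3 adds "Otherwise, efficacy analysis will be restricted to the full analysis set".

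Section 6.4.2 takes this into the extensions: "In general, the same statistical methodology as described for the 24-week treatment period will be used". It also announces an analysis of changes from week 48 to week 104. Table 4 lists "Change in HbA1c from week 48 to week 104" under maintenance of efficacy, with matching entries for FPG and weight, and it lists HbA1c changes from week 24 to week 48 and from week 24 to week 104. Nothing in the protocol exempts these variables from the carry-forward or limits them to patients not yet censored at the starting visit.

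**The concern.** A change between two late visits is meant to show whether the effect lasts. If one earlier measurement stands in for both visits, the difference is zero because of the rule and says nothing about the patient. The zeros enter the mean as if they were observed stability.

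This can plausibly affect many patients. Entry requires HbA1c between 7.5% and 10.5%, and in extension period I up-titration is to be considered "if HbA1c measured by central laboratory exceeds 8% at any point of the 24 weeks double-blind extension period", or on fasting glucose criteria. Anyone up-titrated by week 48 is affected, as is anyone withdrawn by then if LOCF is carried into the extensions. What is at stake is the stated extension objective, maintenance of efficacy to week 48 and week 104, both within each arm and against placebo.

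**Working it through.** **Inputs from the protocol.** 808 randomised and about 14% withdrawn by week 48 (Section 6.5). The carry-forward and LOCF rules are those set out above. On-treatment HbA1c and FPG samples fall at weeks 1, 4, 8, 12, 16, 20, 24, 32, 40, 48, 52, 65, 78, 91 and 104 (Table 5). Weight is measured at the same visits (Table 1).

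**Inputs not in the documents, assumed here.** The share u of non-withdrawn patients up-titrated by week 48, taken from 0 to 50%. A true mean rise in HbA1c of 0.30% from week 48 to week 104, for illustration.

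**Step 1, the protocol's own figure.** 808 × (1 − 0.14) = 694.9, which agrees with the stated figure of about 700 patients to be offered extension period II.

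**Step 2, the rule.** Let T be the week of the last usable value and Y(w) the measurement at week w. The analysed change from week 48 to week 104 is Y(min(104, T)) − Y(min(48, T)).
- T ≤ 48: Y(T) − Y(T) = 0.
- T ≥ 52: Y(T) − Y(48), which is not zero by rule.

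Applied to simulated HbA1c paths on this schedule, the rule gave exactly 0 in every path for each cut-off from week 1 to week 48, and in none for cut-offs at week 52 or later. By the same algebra, the HbA1c changes from week 24 to weeks 48 and 104 are zero when T ≤ 24.

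**Step 3, share of forced zeros.** Share = 0.14 + 0.86 × u.

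**Step 4, dilution.** Reported mean change = (1 − share) × true change. If patients withdrawn before week 48 are left out, it is (1 − u) × true change.

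| u | Forced zeros | Of 808 | True 0.30% reported as | Withdrawn left out |
|---|---|---|---|---|
| 0% | 14% | 113 | 0.26% | 0.30% |
| 10% | 23% | 183 | 0.23% | 0.27% |
| 20% | 31% | 252 | 0.21% | 0.24% |
| 30% | 40% | 322 | 0.18% | 0.21% |
| 40% | 48% | 391 | 0.15% | 0.18% |
| 50% | 57% | 461 | 0.13% | 0.15% |

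The formula assumes the same mean rise in patients with and without a forced zero. It also credits everyone else with the full rise, although a patient cut off between weeks 52 and 91 has an earlier value labelled week 104.

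**Step 5, between arms.** Take an equal true rise of 0.30% in both arms, 14% withdrawn in each, and assumed up-titration of 40% on placebo and 20% on dapagliflozin.
- Placebo: 0.30 × 0.86 × 0.60 = 0.155%.
- Dapagliflozin: 0.30 × 0.86 × 0.80 = 0.206%.

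A spurious difference of 0.05% appears, and it runs against dapagliflozin. With equal rates (20% in both arms) it vanishes.

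**The case against.** The strongest reply is that these analyses carry little inferential weight. Section 6.1 calls them exploratory and supportive, Section 3.6.2 calls them supplemental, and Section 6.4.2 limits them to point estimates and confidence intervals. That stands, and it sets the severity.

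The withdrawal half is also less firmly fixed than the up-titration half. LOCF appears in a set definition written for the 24-week period, and Section 6.4.2 extends the methods only in general terms. An SAP could restrict the week 48 to week 104 set to patients who entered extension period II. The last column of the table covers that case. The up-titration zeros remain.

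Some mitigation exists. Insulin-dose endpoints are not censored at titration, so deterioration met with more insulin shows there. Changes from baseline to weeks 48 and 104 may be frozen at an early value, but they are not zero by rule. The HbA1c summary in Section 6.4.1 at the insulin-dose time points may carry over to the extensions. It covers HbA1c only, however, and it leaves any LOCF zeros after withdrawal in place.

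Finally, censoring at up-titration is a coherent way to estimate the effect without added insulin, and values observed after up-titration answer a different question. That is a fair argument against replacing the censored analysis of change from baseline. It does not justify subtracting a value from itself and averaging the result as a change.

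**Conclusion.** The point holds as a should-fix. For HbA1c, FPG and weight, a last usable value at or before week 48 forces a zero change from week 48 to week 104. For HbA1c, a last usable value at or before week 24 does the same to the changes from week 24. The zeros arise in every arm and pull each within-arm change towards no change. Under the stated assumptions, 14 to 57% of the full analysis set is affected, and a true rise of 0.30% is reported as 0.26 to 0.13%. The real size depends on an up-titration rate that the documents do not give. Crossing a trigger only obliges the investigator to consider up-titration, and an increase counts only if it exceeds both 5 IU and 10% of the baseline dose.

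Three stronger readings are tempting, and the documents do not support them:
- That the rule manufactures durability in favour of dapagliflozin. With equal true drift and more up-titration on placebo, it makes dapagliflozin look less durable relative to placebo.
- That the 7.5% and 7.0% HbA1c triggers make these zeros common. They apply from Visit 14 (week 52), after the starting visit, so a patient up-titrated on such a result carries a value from week 52 or later.
- That the trial's main conclusion is at risk. The confirmatory part is the first 24 weeks, and no primary or key secondary comparison uses these variables.

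**What to change.** In Section 6.4.2, state that changes from week 24 or week 48 are computed only in patients with values actually observed at both visits, never from a value carried across the starting visit. Report the number contributing per arm. Say explicitly whether a measurement taken after up-titration counts as observed for this purpose.

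Add an analysis of observed HbA1c, FPG and weight at Visits 10 to 12 and 14 to 18 regardless of up-titration, using a repeated-measures model, and show it beside mean insulin dose. Keep the censored LOCF analysis for change from baseline.

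The cost is protocol and SAP wording and one more set of tables. All the measurements are already scheduled, and no titration rule changes. There are two downsides to state in the report. The both-visits analysis describes a smaller, selected set of patients, and the observed-value analysis includes the effect of added insulin, which is why the insulin-dose table belongs next to it.

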3.2 Rationale and risk/benefit assessment

3.2.1 Rationale for study design, doses and control groups

3.2.1.1 Study design and regulatory requirement

The current trial is designed to demonstrate the efficacy and safety of dapagliflozin when used as add-on therapy to insulin in patients with type 2 diabetes inadequately controlled with insulin alone for at least 8 weeks prior to enrolment. Specifically, this study will investigate if treatment with dapagliflozin as add-on to insulin is beneficial for patients with type 2 diabetes as compared to placebo as add-on therapy to insulin. A superiority comparison will be applied for this randomized, double-blind, placebo-controlled study. This protocol incorporates the relevant features of the Committee for Proprietary Medicinal Products' guidance for investigations of diabetes ([CPMP 2002](#)) with regard to control group, duration of treatment, choice of study population, and choice of outcome variables.

Short term clinical studies of up to 12 weeks duration have been completed using all three doses of dapagliflozin as a starting dose in patients with type 2 diabetes. The clinical experience gained to date in these short term studies demonstrates that a titration regimen is not necessary for the clinical use of dapagliflozin. In addition, the three doses of dapagliflozin are being tested independently as starting doses in other ongoing long term phase III studies of up to two years in duration.

